Colonoscopy in the prone position for patients with BMI >30 is superior to standard left lateral decubitus position

Protocol: IRB-HSR 20078

10/4/2017

Page 0 of 5 Version: 10-4-17

PROTOCOL

Background

1. Provide the scientific background, rationale and relevance of this project.

In the United States, colonoscopy has become the most commonly used screening test for colorectal cancer (7). Colonoscopy is typically performed with the patient starting in the left lateral decubitus position, however there is little data to support this practice. Throughout the colonoscopy, patients are often re-positioned in a variety of ways (shifted into a prone or supine position) to facilitate passage of the endoscope. There are a number of patient characteristics that are known to make colonoscopy more technically challenging necessitating positional changes, including female gender, prior abdominal or pelvic surgery, and BMI > 30. Despite these differences, there is minimal data in the literature to guide endoscopists regarding which patient positioning strategies to employ based on individual patient characteristics. It is estimated that 35% of adult men and 40.4% of adult women were identified during recent a recent study to fall into the "obese" category with BMI \geq 30 (8). Patient repositioning and application of pressure to the abdomen, another frequently used technique, can be particularly difficult for endoscopy staff to employ in a sedated, obese patient (9). The time from starting the colonoscopy until the colonoscope is advanced to the cecum, cecal intubaton time, is standardly recorded during colonoscopy. Longer cecal intubation times reflect more technically challenging procedures.

Several published studies investigating the Trendelenburg position (1) suggested decreased cecal intubation time, particularly in patients with significant sigmoid diverticulosis. However this technique revealed the increased occurrence of transient oxygen desaturation in obese patients which limited its use in this population. The right later decubitus position is frequently used to help advanced of the endoscope within the cecum or into the terminal ileum (2). In particular, women and patients who have previously undergone abdominal surgery seemed to benefit from right lateral decubitus position with improved cecal intubation times (4).

The prone position has been shown to successfully reduce ileal intubation times in a study involving 150 patients (3) regardless of BMI.

One study in particular (5) completed in 2012 at the North Texas VA Medical center showed patients with a BMI of >30 had shorter cecal intubation times and decreased need for re-positioning when colonoscopy was performed in the prone position. This study patient population was limited to all male veterans. The proposed mechanism is that of redistribution of abdominal pressure prevent loop formation, which should extrapolate to female patients as well.

This study reported no procedural sedation or airway related complications. It has been postulated that the prone position may actually be associated with a lower risk of obstructive apnea during sedation since the tongue is less likely to fall back (6).

Cecal intubation time is frequently used as a target metric for improvement in endoscopy as a shorter procedure in turn reduces length of time sedation is required.

Objectives/Hypothesis

Prone position of both male and female patients with BMI >30 will be less technically difficult in the prone position than in the more commonly used left lateral decubitus position. This will result in a more comfortable

Page 1 of 5 Version: 10-4-17

patient experience as well as a reduced procedure times resulting in decreased need for sedation. There is no expected difference in complication rate for either position.

Study Design: Biomedical

1. Will controls be used?Yes

► IF YES, explain the kind of controls to be used.

Study participants will be randomized to either left lateral decubitus or prone position at the time of colonoscopy. Patients randomized to left lateral decubitus position will be consider the controls.

2. What is the study design?

Randomized control study

3. Does the study involve a placebo?No

Human Participants

Ages: 18-90

Sex: Any

Race: Any

Subjects- see below

INSTRUCTIONS: For question 1-4 below insert an exact #. Ranges or OPEN is not allowed. This # should be the maximum # you expect to need to enroll (i.e. sign consent) If you are only collecting specimens the number of participants should equate to the # of specimens you need. If you are collecting only data from a chart review the number should designate the number of subjects whose medical records you plan to review. Age/ Sex/Race criteria should designate the demographics of participants from whom you will obtain the specimen/data.

1. Provide target # of subjects (at all sites) needed to complete protocol.150

- 2. Describe expected rate of screen failure/ dropouts/withdrawals from all sites. Expect 20% of screened patients will qualify and consent to participate in the study
- 3. How many subjects will be enrolled at all sites? 150
- 4. How many subjects will sign a consent form under this UVa protocol? 150

Inclusion/Exclusion Criteria

1. List the criteria for inclusion

- Willingness and ability to comply with scheduled visits and study procedures.
- BMI >30
- Undergoing screening or diagnostic colonoscopy at UVA as part of clinical care

Page 2 of 5 Version: 10-4-17

• Adults aged 18-90

2. List the criteria for exclusion

- Pregnant women (self reported).
- Cognitively impaired
- Hx colonic resection
- Cannot lay in prone position
- Hx of colon malignancy
- Procedure aborted due to bowel prep
- Severe pulmonary problems (baseline oxygen use)
- Inablility to consent

3. List any restrictions on use of other drugs or treatments.None

Statistical Considerations

1. Is stratification/randomization involved?

Yes – Randomization only

► IF YES, describe the stratification/ randomization scheme.

Study participants will be randomized to either left lateral decubitus or prone position at the time of colonoscopy. Randomization order will be computer generated with allocation concealment using sequentially numbered, sealed envelopes. Patients and co-investigators performing colonoscopy will not be blinded.

► IF YES, who will generate the randomization scheme?

____x_ Other: PI

2. What are the statistical considerations for the protocol?

-Prospective Randomized trial.

-Enrolled participants will be randomized to colonoscopy in the left lateral decubitus or prone position. -The primary endpoint is cecal intubation time. Cecal intubation time is standardly recorded during all colonoscopies. Null hypotheses is that there will be no difference in cecal intubation times between the 2 groups. To detect an effect size of 60 seconds difference between the 2 groups (left later decubitus vs prone position) with a standard deviation of 120 seconds for the average colonoscopy = ~125 total study participants - 63 per group (alpha = 0.05 / type I error rate). Type II error rare: 0.2. Goal to enroll 150 to adjust for variability in cecal intubation time.

-Two secondary endpoints will be measured: complication rate in each group as well as sedation use. -Complications during the procedure will be noted and charts will be reviewed for complications occurring within 30 days of the procedure. Complications will be recorded as either present vs absent. -Sedation use is standardly recorded during all procedures. This is record as mg of fentanyl and mg of midazolam. Page 3 of 5 Version: 10-4-17

3. Provide a justification for the sample size used in this protocol.

To detect an effect size of 60 seconds difference between the 2 groups with a standard deviation of 120 seconds for the average colonoscopy = 125 total study participants - 63 per group (alpha = 0.05). Goal to enroll 150 to adjust for variability in cecal intubation time.

4. What is your plan for primary variable analysis?

T test for comparison of mean cecal intubation time in each group.

5. What is your plan for secondary variable analysis?

T test for comparison of mean amount of sedation used in each group as well as number of adverse events/ complications

6. Have you been working with a statistician in designing this protocol?No

7. Will data from multiple sites be combined during analysis? no

Study Procedures-Biomedical Research

1. What will be done in this protocol?

Patients that have been scheduled for colonoscopy will undergo chart review by the co-investigator (GI attening) scheduled to perform the colonoscopy or the GI fellow. Patients who meet inclusion criteria will be invited to participate at the time consent is obtained for the colonoscopy. Participants will then be randomized to one of two colonoscopy starting positions.

After randomization, patients will begin the colonoscopy in either the prone position or left lateral decubitus position.

Adjusting patient starting position to the prone rather than left lateral decubitus position is not expected to result in any additional risk to the patient beyond the standard risks related to colonoscopy. It is common practice to re-position the patient during endoscopy (including supine and prone positions) and some endoscopists commonly employ prone starting position for obese patients, although there is no estimate in the literature as to the prevalence of this practice.

No additional interventions will be performed for research purposes.

During the colonoscopy, the endoscopist will be allowed, as usual, to adjust patient position as needed to complete the procedure. Cecal intubation time, amount of sedation used, and any intra-procedural complications (hypoxia, hypotension, etc) will be recorded for data analysis. This information is standardly recorded in the procedure report in the patient's medical record. The study will not affect any interventions performed during the colonoscopy such as polyp removal or biopsies as, clinically indicated. Per endoscopy unit protocol, patients will be monitored in the recovery area and discharged home with supervision. The study requires no further direct patient interaction after the colonoscopy is completed. Charts will be reviewed at 30 days to assess for any delayed and unexpected complications.

Page 4 of 5 Version: 10-4-17

2. If this protocol involves study treatment, explain how a subject will be transitioned from study treatment when they have completed their participation in the study. N/A

Subject Compliance with Study Procedures

- 1. **Explain how the study team will monitor the subject for compliance with the study procedures.** Patient compliance is only requiring at the time of the colonoscopy. The performing endoscopist will note of patient is not able to comply with starting position per randomization.
- 2. Describe criteria for when a subject is considered to be non-compliant with study procedures. N/A

Bibliography

- 1) Colonoscopy in the tilt-down position Weinstock, Leonard B.Early, Dayna S. et al. Gastrointestinal Endoscopy , Volume 80 , Issue 4 , 746
- Achieving cecal intubation in the very difficult colon. Rex DK. Gastrointest Endosc. 2008 May;67(6):938-44. doi: 10.1016/j.gie.2007.12.028. Review.
- The prone 12 o'clock position reduces ileal intubation time during colonoscopy compared to the left lateral 6 o'clock (standard) position.
 De Silva AP, Kumarasena RS, Perera Keragala SD, Kalubowila U, Niriella M, Dassanayake AS,

Pathmeswaran A, de Silva HJ.

BMC Gastroenterol. 2011 Aug 4;11:89. doi: 10.1186/1471-230X-11-89.

- Right Or Left in COLonoscopy (ROLCOL)? A Randomized Controlled Trial of Right- versus Left-Sided Starting Position in Colonoscopy. Vergis N, McGrath AK, Stoddart CH, Hoare JM. Am J Gastroenterol. 2015 Nov;110(11):1576-81. doi: 10.1038/ajg.2015.298. Epub 2015 Sep 29.
- 5) Prone positioning of obese patients for colonoscopy results in shortened cecal intubation times: a randomized trial.

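### Does the trial need a planned estimate in women, given that the earlier prone-position trial enrolled only men?

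*Combined protocol and SAP*

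**What the plan says.** The Background reports that the earlier randomized trial found shorter cecal intubation times with prone positioning above BMI 30, and adds: "This study patient population was limited to all male veterans". It then gives a mechanism, a shift of abdominal pressure that keeps loops from forming, "which should extrapolate to female patients as well". Objectives/Hypothesis states: "Prone position of both male and female patients with BMI >30 will be less technically difficult in the prone position". Human Participants admits any sex and sets no quota.

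The Background also lists features that make colonoscopy harder, "including female gender, prior abdominal or pelvic surgery, and BMI > 30", and notes "minimal data in the literature to guide endoscopists regarding which patient positioning strategies to employ based on individual patient characteristics". Of another position it reports that "women and patients who have previously undergone abdominal surgery seemed to benefit from right lateral decubitus position".

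Statistical Considerations item 1 specifies randomization without stratification. Item 2 sets the null: "Null hypotheses is that there will be no difference in cecal intubation times between the 2 groups". Item 4 gives the primary analysis: "T test for comparison of mean cecal intubation time in each group". Item 5 plans t tests by arm for sedation and complications. No analysis by sex is listed.

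**The concern.** The Background names the all-male sample as the limit of the earlier trial and bridges to women by argument, not by data. The hypothesis then mentions both sexes. A reader may infer that women are what this trial adds and expect an estimate in women. None is planned.

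A pooled difference is an average over the sexes weighted by their shares. A significant result could in principle come mostly from men, and the authors might then write that prone positioning has been shown to work in women. What would be at stake is the breadth of the conclusion: a claim about women resting on a number that does not isolate them.

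**Working it through.** **1. The plan's own figure.** Inputs from Statistical Considerations items 2 and 3: difference 60 s, SD 120 s, alpha 0.05 (taken as two-sided), type II error 0.2.

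n per group = 2 × (1.960 + 0.842)² × 120² / 60² = 2 × 7.85 × 4 = 62.8, so 63 per group. This matches the protocol. A one-sided alpha would give 50, which does not match. At 150 patients (75 per arm), power for 60 s is 86.0% by the noncentral t. The design is sized for the pooled comparison, and item 4 analyses the pooled comparison.

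**2. What the pooled test can conclude.** Let p be the share of women. The protocol gives no figure, so 30%, 50% and 60% are assumed. The pooled effect is (1 − p) × effect in men + p × effect in women.

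At 75 per arm the smallest significant difference is t × 120 × √(4/150) = 1.976 × 19.60 = 38.7 s. If women gained nothing, an observed 38.7 s would correspond to 38.7/(1 − p) = 55.3, 77.4 or 96.8 s in men. That is an arithmetic possibility; nothing in the documents suggests it.

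Even then the pooled conclusion is not false. With a true 60 s in men and 0 s in women, the average effect is 60 × (1 − p) = 42, 30 or 24 s. Rejecting a null of no difference between positions is correct in each case. Under a true null in both sexes, randomization protects the type I error whatever the sex mix.

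**3. Whether the documents commit to a claim about women.**

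- The title and eligibility criteria define the population by BMI above 30, and the null names two groups defined by position.
- The phrase in Objectives/Hypothesis that covers both sexes can be read as describing who is enrolled. It is not set out as two hypotheses, and neither sex has its own endpoint, alpha or sample size.
- The extrapolation sentence argues for admitting women, and the trial does admit them.
- The mechanism given is not specific to sex, and no section says that the prone effect differs by sex.
- The sentence on right lateral positioning concerns another position and names surgical patients together with women. The list of difficulty factors does the same. On that reasoning, estimates by surgical history would be required too.

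**4. What an estimate in women would deliver.** Half-width = t × 120 × √(4/number of women). Standard error (SE) of the interaction = 120 × √(4/women + 4/men). Total 150, 1:1 within sex, SD 120 s in both sexes.

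| Assumed share of women | Women | 95% half-width in women | Power for 60 s in women | Interaction SE | Power for a 60 s interaction |
|---|---|---|---|---|---|
| 30% | 45 | 72.2 s | 37% | 42.8 s | 29% |
| 50% | 75 | 55.2 s | 57% | 39.2 s | 33% |
| 60% | 90 | 50.3 s | 65% | 40.0 s | 32% |

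Simulation (75 per arm, normal outcomes, SD 120 s, 60 s true effect in men, 60,000 trials per setting) shows how such a table would read once the pooled test is significant in favour of prone. Results are for 30%, 50% and 60% women.

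- True effect 60 s in women: their interval lies wholly above zero in 41%, 64% and 74% of trials, so it misses a real benefit in the rest.
- True effect 0 s in women: their interval contains both 0 and 60 s in 74%, 70% and 69%. It lies wholly above zero in 4.2%, 7.1% and 10.5%, against a nominal 2.5% in that direction.

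The table would often fail to separate no benefit from the design benefit, and after a positive trial it would mislead somewhat more often than its nominal rate.

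**The case for a change.** The strongest case for the concern is that sex is not an arbitrary subgroup here. It is the one characteristic for which the protocol names a gap in the earlier evidence and fills it by assumption. The pooled mean cannot test that assumption. A descriptive estimate by sex would need two sentences in item 4 and no extra patients or data, and fixing it in advance would commit the investigators to report it whatever it shows.

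Part of this stands. No planned output isolates women, and a report that claimed a separately demonstrated benefit in women would go beyond the planned analysis. Planning such an estimate would be reasonable practice.

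It does not show a fault in the plan. The overreach would be in a sentence that the protocol does not announce. The data needed for a later estimate by sex are those the trial already collects. The earlier trial was also confined to veterans, so the new trial widens the population in more than one respect, and widening it does not oblige the trial to estimate the effect separately in each added group.

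**Conclusion.** The concern does not hold. The null, the sample size and the primary t test all address the same comparison of positions in a mixed-sex population with BMI above 30. On this point, following the plan as written gives a valid test and a conclusion at the level the protocol states. Type I error is unaffected, and so is the 86% power for 60 s at 150 patients. What remains is a preference for an optional descriptive table, with a 95% half-width in women of about 50 to 72 s and 29% to 33% power for a 60 s interaction.

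The sex-specific figures assume 30% to 60% women, an SD of 120 s in each sex and 1:1 allocation within sex. The protocol gives the SD only for the average colonoscopy and does not give the share of women. The verdict itself rests on reading the hypothesis as naming the enrolled population, which fits the title and the null. If the investigators meant to claim a separately demonstrated benefit in women, that claim would need its own analysis.

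### An abort for poor bowel preparation is listed as an exclusion, although the colonoscopy starts only after randomisation; on its ordinary reading this drops patients who already have an arm

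*Combined protocol and SAP*

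**What the plan says.** Inclusion/Exclusion Criteria, item 2, includes "Procedure aborted due to bowel prep". The other entries in that list describe the patient and can be assessed before allocation. This one is an event of the procedure.

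Study Procedures, item 1, gives the order: chart review, consent, randomisation, procedure. Its wording on the last step is "After randomization, patients will begin the colonoscopy in either the prone position or left lateral decubitus position". Statistical Considerations, item 1, adds that allocation is by sealed envelope and that "Patients and co-investigators performing colonoscopy will not be blinded".

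On the data:

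- **Primary endpoint.** Background defines cecal intubation time as "The time from starting the colonoscopy until the colonoscope is advanced to the cecum". Statistical Considerations, item 2, says "Cecal intubation time is standardly recorded during all colonoscopies", and item 4 plans a "T test for comparison of mean cecal intubation time in each group".
- **Secondary endpoints.** Item 2 also says "Sedation use is standardly recorded during all procedures" and that "charts will be reviewed for complications occurring within 30 days of the procedure".

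No section defines an analysis population, names who decides to abort or by what standard, or says what happens to the data of an aborted case. The answer on screen failure and dropout gives only the screening yield (20%).

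**The concern.** A procedure can be aborted only once it is under way, and here that is after the envelope has been opened. An exclusion that acts at that point lets an event after allocation decide who counts as a trial patient. If the decision to abort is the endoscopist's, which is plausible but not stated, it is made with knowledge of the arm.

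Two things are at stake. The first is the loss of sedation and complication data that would exist for these patients, and complications are the trial's safety comparison. The second is the comparability of the arms, if the threshold for giving up on a poorly prepared colon differs between positions.

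**Working it through.** **1. The plan's own sample size.** Inputs from Statistical Considerations, items 2 and 3: difference 60 s, SD 120 s, alpha 0.05, type II error 0.2. Two-sided normal approximation:

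n per group = 2 × (1.960 + 0.842)² × (120/60)² = 2 × 7.849 × 4 = 62.8, so 63 per group and 126 in total.

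This reproduces the stated 63 per group and roughly 125 in total. Enrolment is set at 150, or 75 per arm if allocation is equal, as the 63 per group implies.

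**2. Patients affected.** The documents give no abort rate, so 5% and 10% are assumptions.

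- 150 × 0.05 = 7.5 patients
- 150 × 0.10 = 15 patients

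These patients would have sedation records and a 30-day chart review, and would be lost to both secondary comparisons if excluded.

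**3. Power of the primary test.** Noncentral t, two-sided 0.05, standardised difference 60/120 = 0.5:

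| Times lost | Per arm | Power |
|---|---|---|
| 0% | 75 | 86.0% |
| 5% | 75 × 0.95 = 71.25 | 84.2% |
| 10% | 75 × 0.90 = 67.5 | 82.2% |

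**4. Bias in the primary test.** Preparation quality is fixed before randomisation, so aborts should be balanced unless the decision depends on the arm. For an illustration, suppose there is no true effect, a share h of patients has hard preparation with times 180 s longer, and the SD is 120 s within each type of patient. All hard-preparation patients are aborted in prone, and a share p of them in left lateral. None of these figures is in the documents. Left lateral then keeps some slow patients and prone keeps none:

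bias = 180 × h(1 − p) / (1 − hp)

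- h = 0.05, p = 0.6: 180 × 0.02/0.97 = 3.7 s
- h = 0.10, p = 0.5: 180 × 0.05/0.95 = 9.5 s
- h = 0.05, p = 0.8: 180 × 0.01/0.96 = 1.9 s
- h = 0.05, p = 0.9: 180 × 0.005/0.955 = 0.9 s
- p = 1 (equal aborts): 0 s

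With r the share of hard-preparation patients among those kept in left lateral, that arm's variance is 14,400 + r(1 − r) × 180².

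- First case: r = 0.02/0.97 and the variance is 15,054. The standard error is √(14,400/71.25 + 15,054/72.75) = 20.2 s. The chance of falsely declaring prone superior is P(Z > 1.96 − 3.71/20.2) = 3.8%, against a nominal 2.5%.
- Second case: the variance is 16,016. The standard error is √(14,400/67.5 + 16,016/71.25) = 20.9 s, and P(Z > 1.96 − 9.47/20.9) = 6.6%.
- Arms reversed: P(Z > 1.96 + 3.71/20.2) = 1.6% and P(Z > 1.96 + 9.47/20.9) = 0.8%.
- The two milder contrasts give about 3.1% (p = 0.8) and 2.8% (p = 0.9).

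**5. What a change of wording alters.** A procedure aborted before the cecum has no cecal intubation time by the protocol's own definition. The results in step 4 are therefore the same whether such a patient is called excluded or missing. Keeping the patient restores the secondary data, plus a cecal intubation time in any case aborted after the cecum was reached.

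**The case against.** The strongest reply is that the item sits in an eligibility list whose other entries apply before allocation. Consent and randomisation take place at the time of the colonoscopy, so the authors may have meant cases called off for poor preparation before the envelope is opened. That would be harmless. The reading is possible, but the word used fits it less well and no preparation check before randomisation is described. The text needs clarifying under either reading.

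A second reply is that nothing states that these patients leave the analysis. Study Procedures says that time, sedation and complications are recorded for analysis and charts are reviewed at 30 days, with no exemption for aborted cases. This stands in part. A reader might infer that the plan expressly removes them from all three comparisons. It does not: removal is what an exclusion ordinarily means, and no section says that they are kept.

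A third reply is that the effect is small and the fix leaves the t test where it was. This also stands. A reader might infer a bias in favour of prone, but the documents give no reason to expect more aborts in one arm. The larger figures in step 4 need an extreme contrast in one chosen direction.

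**Conclusion.** The point holds in limited form. On its ordinary reading, the criterion excludes randomised patients during an unblinded procedure, and nothing in the documents keeps them in the analysis.

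The avoidable cost falls mainly on the sedation and complication comparisons. Its size rests on an assumed abort rate, since none is given. For the primary endpoint, any bias depends on abort decisions differing by arm. It could go either way and is likely to be small against the 60 s target difference. The enrolment margin covers the loss of power over the range examined, so the trial should not be called underpowered on this account.

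Severity is minor to moderate. Confidence is moderate, because the intended timing of the criterion and the person who decides are not stated.

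**What to change.** 1. Delete the item from the exclusion list, or reword it so that it applies only to cases called off for bowel preparation before the envelope is opened.
2. State that every randomised patient is analysed in the assigned arm for each endpoint with a recorded value. Aborted cases then stay in the sedation and complication comparisons, and any recorded cecal intubation time stays in the primary t test. Say plainly that an abort before the cecum leaves the time missing.
3. Report aborted procedures by arm, with reasons, so that an imbalance can be seen.

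The cost is a short amendment and one line in the report. Sample size and primary test do not change. The downside is a little added noise in the sedation comparison from shortened procedures.

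A rank analysis that places cecum-not-reached cases last is optional. It counts preparation failures unrelated to position as bad outcomes. In simulation, its power for 60 s was about 76% at 5% aborted and 66% at 10%, so it should be no more than a sensitivity analysis.

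### Optional improvement: the unadjusted t test is valid, but a prespecified model with sex and prior abdominal or pelvic surgery could add modest precision at little cost

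*Combined protocol and SAP*

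**What the plan says.** Statistical Considerations, item 4, sets the primary analysis as "T test for comparison of mean cecal intubation time in each group". No covariates are named, and item 1 of the same section describes randomisation without stratification. Neither the design nor the analysis uses baseline information.

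The Background lists patient characteristics that make colonoscopy more demanding, "including female gender, prior abdominal or pelvic surgery, and BMI > 30", and ties difficulty to the primary endpoint: "Longer cecal intubation times reflect more technically challenging procedures".

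The eligibility criteria determine which of these three factors still vary:
- **BMI above 30** is met by every participant, so the threshold itself does not vary.
- **Sex** varies. The Objectives/Hypothesis section speaks of "Prone position of both male and female patients with BMI >30 will be less technically difficult", and either sex may enrol.
- **Prior surgery** varies, but over a narrower range. "Hx colonic resection" is an exclusion, and it is the only surgery listed as one.

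Study Procedures, item 1, places the eligibility check before randomisation: "Patients that have been scheduled for colonoscopy will undergo chart review by the co-investigator".

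**The concern.** If a baseline factor predicts the outcome within each arm, an unadjusted comparison of means leaves that variation in the error term. The protocol names two such candidates and links them to its primary endpoint in general terms, then does not use them. If the link is strong enough, the same 150 patients would give a narrower interval for the effect of starting position. At stake is precision only. The validity of the comparison and the type I error are not in question.

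**Working it through.** **Inputs from the plan** (Statistical Considerations, items 2 and 3): difference 60 s, SD 120 s, alpha 0.05, type II error 0.2, 63 per group, enrolment goal 150. Sidedness is not stated. R2 for sex and prior surgery is not given, so a range of 0 to 20% is assumed.

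**Step 1: reproduce the plan's figure.** n per arm = 2 × (1.960 + 0.842)² × (120/60)² = 62.8, rounded up to 63 (126 in total, against about 125 stated). A one-sided test would need 50 per arm, so the plan's figure is two-sided.

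**Step 2: power of the planned t test.** SE = 120 × √(2/n), with a noncentral t on 2n − 2 df.
- 63 per arm: SE 21.38 s, power 79.5% (80.1% by the normal approximation).
- 75 per arm: SE 19.60 s, power 86.0%, 95% CI half-width 38.7 s.

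**Step 3: power of the two-covariate model.** With N = 2n and p = 2, SE = 120 × √(2/n) × √(1 − R2) × √(1 + p/(N − p − 3)), on N − 2 − p df. The last factor charges for chance imbalance in the covariates. For example, at 75 per arm and R2 = 10%: 19.60 × √0.90 × √(1 + 2/145) = 18.72 s.

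| Analysis | 75 per arm: power | 75 per arm: 95% CI half-width | 63 per arm: power |
|---|---|---|---|
| t test | 86.0% | 38.7 s | 79.5% |
| Adjusted, R2 = 0 | 85.6% | 39.0 s | 78.9% |
| Adjusted, R2 = 5% | 87.3% | 38.0 s | 80.9% |
| Adjusted, R2 = 10% | 89.0% | 37.0 s | 82.9% |
| Adjusted, R2 = 20% | 92.2% | 34.9 s | 87.0% |

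Break-even R2 is about 1.4% at 75 per arm and about 1.7% at 63 per arm.

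**Step 4: what such R2 values would require.** Assume 50% women, 30% with prior surgery, and independent factors, each adding *a* seconds (all assumptions). Then R2 = (0.25a² + 0.21a²)/120².
- a = 15 s: R2 0.7%, power 85.8% at 75 per arm (−0.2 points).
- a = 30 s: R2 2.9%, power about 86.5% (+0.5).
- a = 60 s: R2 11.5%, power 89.5% (+3.4).

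**Step 5: compare with the enrolment margin.** Going from 63 to 75 per arm adds 6.5 points (79.5% to 86.0%). For adjustment to add as much, R2 would have to be about 18% at 63 per arm or about 21% at 75 per arm.

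**Step 6: simulation check.** In 20,000 simulated trials per scenario at 75 per arm, adjusted power was 85.5%, 87.1%, 88.7% and 92.0% at R2 of 0, 5%, 10% and 20%. Type I error was 4.8–5.1% adjusted and 4.9–5.2% unadjusted.

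**The case against.** The strongest reply is that nothing needs fixing. The t test is valid, matches the randomisation and exceeds the power target at 150 patients, while the proposed benefit rests on an R2 that the documents lack. The 3.4-point gain in step 4 needs each factor to shift cecal intubation time by 60 s, as much as the treatment effect the trial is sized to detect. At half that shift the gain is 0.5 points. All of this stands, and it is why the point is optional.

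Four stronger readings are tempting, and the documents do not support them.
- **That the t test is biased or wrong.** Randomisation makes the unadjusted comparison valid.
- **That the Background shows these factors drive cecal intubation time.** It reports that "women and patients who have previously undergone abdominal surgery seemed to benefit from right lateral decubitus position with improved cecal intubation times". That describes who benefited from another position, which is effect modification. It does not show that either factor predicts time within an arm, which is what adjustment needs. What remains is the general statement on difficulty, not specific to patients with BMI above 30. The endoscopist may also reposition freely, which could weaken any association.
- **That both covariates are already in hand.** The chart review is for eligibility, and the only surgical item in the criteria is colonic resection. Nothing says that other abdominal or pelvic surgery is recorded. If it is recorded poorly, R2 falls, although the comparison of arms stays unbiased.
- **That adjustment could stand in for the enrolment margin.** The plan states "Goal to enroll 150 to adjust for variability in cecal intubation time". Step 5 shows that this margin adds more power than the model does unless R2 reaches about 18–21%.

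**Conclusion.** This is a cheap improvement and not an error. Keeping the t test as primary would be defensible. At 75 per arm the two-covariate model changes power by about −0.5 points if the factors explain nothing, +1.2 at R2 = 5%, +2.9 at 10% and +6.1 at 20%. The largest loss at 63 per arm is about 0.7 points. The case for adjustment is that this downside is small and bounded, and that the protocol itself names both factors. The figures assume 60 s, SD 120 s, a two-sided 5% test, equal arms and an R2 that must be guessed. They do not bear on how failed cecal intubation is handled.

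**What to change.** Before any outcome is seen, amend Statistical Considerations, item 4:
- Name as primary a linear model for cecal intubation time with three terms: randomised arm, sex, and prior abdominal or pelvic surgery (yes/no, coded no if the chart shows none).
- Report the adjusted mean difference with its 95% CI, and keep the t test as a supportive analysis.
- Take both covariates from the chart review done before randomisation. Add a field for abdominal or pelvic surgery other than colonic resection to the data collected, and record sex.

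No operator term, BMI term or change to the randomisation is proposed.

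The cost is one sentence in the plan, two chart fields and two degrees of freedom. If the factors explain nothing, the 95% CI half-width at 75 per arm grows by 0.3 s.
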